Attendance Phase - Participants in the Attendance Incentive group will receive vouchers for attendance. Participants in the Attendance Information group will not receive vouchers for attendance, however, they will receive a \$20 gift card for attending a half-hour information session. (Participants will be made fully aware that they have only a 50/50 chance of receiving monetary rewards for either Admission phase or Attendance phase.)

- Clients in the Attendance Incentive group will start earning incentives starting on the first Monday following their full induction into the study (informed consent, interview, etc.).
- Incentive group members will receive \$2.50 per day for the first week (\$12.50 total for the week),
- \$3.00 per day for the second week (\$15.00 total),
- \$3.50 per day for the third week (\$17.50 total), and so on. (SEE TABLE 1),
- Voucher amounts increase by \$2.50 per week, each week, if perfect attendance is maintained.
- Upon successful completion of weeks 5, 10 and 15, clients will receive a bonus voucher worth \$10. Bonus vouchers will only be awarded if the client maintains perfect attendance for that entire week.
- During the 22 weeks, if a client has an unexcused absence, the value of the voucher is reset to the beginning amount (meaning \$2.50/day for 2 weeks (10 days if

residential, 6 contacts for outpatient). If attendance is perfect for the entire reset, the client may begin earning at the next highest earning level, above the one he had previously achieved.

- Attendance will be recorded daily (reinforcement vouchers will be granted for a maximum of 90 times).
- Symbolic colorful vouchers will be awarded 5 days/week for the first 12 weeks and 3 days/week for weeks 13-22, regardless of when the client actually switches to outpatient status.
- Clients will receive access to their earnings on the following Tuesday via their PIP account.
- Voucher earnings may be accrued over time for a large pay-off at the end, and can be tracked via the 'Weekly Voucher Earnings Ledger.'

TABLE 1
22 Week - ATTENDANCE INCENTIVE SCHEDULE

Intervention Week	Amount per day when vouchers are awarded 5 days/week	Amount per day when vouchers are awarded 3 days/week	Amount per Week Possible	Cumulative Earnings (if perfect attendance)
1	\$2.50		\$12.50	\$12.50
2	\$3.00		\$15.00	\$27.50
3	\$3.50		\$17.50	\$45.00
4	\$4.00		\$20.00	\$65.00
5	\$4.50		\$32.50	\$97.50
6	\$5.00		\$25.00	\$122.50
7	\$5.50		\$27.50	\$150.00
8	\$6.00		\$30.00	\$180.00

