At the beginning of each month, treatment staff at the SATF SAPs will provide the interviewer with a list of clients who are expected to parole that month and who have received a referral to the Walden House community program. The interviewer will meet with potential participants in a private office to screen for eligibility, review study procedures, obtain informed consent, and complete study-related forms.

As part of the recruitment process, the interviewer will complete the following forms with the participant (before the baseline interview and randomization):

- *Informed Consent Form.* The Informed Consent Form, which was approved by the UCLA Institutional Review Board (IRB), includes a statement that the study involves research, an explanation of the purposes and procedures of the study, and an estimate of the expected duration of participation. It states the voluntary nature of the study, describes possible risks of participation, anticipated benefits to the participant, confidentiality procedures to be followed, and an explanation of whom to contact with questions. After reviewing the consent form, the interviewer will ask potential participants a set of questions to determine whether they are able to provide informed consent. If so, the interviewer asks the client to sign the Informed Consent Form, countersigns the form, and gives a copy to the participant. Those who do not understand the consent process will not be eligible to participate in the study. (From experience in other ISAP studies, few, if any, such exclusions will occur.) Since the prospect of receiving additional incentives in the Attendance Phase may itself increase show-up rates, the consent form for the Admission Phase will not describe the Attendance Phase, only that they may be asked to participate in future studies. (See section on Protection of Human Subjects below for more detail.)

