- *Locator Form.* This form is used during the Attendance Phase to collect information that assists research staff in tracking clients for follow-up interviews. The form asks for such information as date of birth, Social Security number, driver's license, vehicle license number, locations of hangouts, and addresses and phone numbers of family and friends (see further details below under *Tracking and Locating*). During the Admission Phase only a brief locator form is used. The brief locator form is used to collect an address to send the Admission Phase gift card. This form is also used to record the client's expected parole date so that research staff will know when to start tracking the client's admission (or not) to Walden House.

During both the Admission and Attendance phases, a brief description of that phase's incentive program and its philosophy is provided after completion of the informed consent form and locator form, but before the structured baseline interviews. The goals are to -

- Orient applicants to what will happen in treatment.
- Create an atmosphere of optimism about treatment outcome.
- Make applicants feel hopeful about improving their life situation.
- The intake worker should also explain that –
 - The program is confidential; everything discussed or written remains private.
 - Each person who signs up to be in the study has a 50/50 chance of gaining entry into the incentives group for admission, and another 50/50 chance of gaining entry into the attendance incentives group following entry into the Walden House program. Only half of the people in the study will receive vouchers.
 - The Attendance intervention lasts for up to 22 weeks.
 - The client will begin earning incentives (only if he is in the incentive group) beginning on the Monday following his entry into the Attendance phase of the study
- The intake worker also provides a very brief description of the voucher incentive program.

If you are randomly selected to participate in the information group, you will attend a half-hour session on why it is helpful to stay in treatment, receive a brochure with that same information and receive a Target gift card for \$20.

If you are randomly selected to participate in the incentives program:

“When you attend treatment, you will earn vouchers. These vouchers indicate the amount of money you earn for treatment participation. You can accumulate

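### The shared intake description tells Admission Phase recruits of the attendance incentives that the Admission consent form is meant to leave out, so H1 tests the $50 voucher against a changed background

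*Protocol*

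**What the plan says.** All but the last item below come from the Protocol, Recruitment - Intake Procedures, in the text following the sample recruitment script.

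- **Informed Consent Form item (Admission Phase).** The reason for silence is given as "Since the prospect of receiving additional incentives in the Attendance Phase may itself increase show-up rates". The means is that "the consent form for the Admission Phase will not describe the Attendance Phase, only that they may be asked to participate in future studies".
- **Order of steps.** For Admission recruits, "the interviewer will complete the following forms with the participant (before the baseline interview and randomization") is the stated sequence.
- **Description after the Locator Form item.** "During both the Admission and Attendance phases, a brief description of that phase's incentive program and its philosophy is provided", after the consent and locator forms and before the structured baseline interviews.
- **What the intake worker should explain.** Each person who signs up has an even chance of the admission incentive and "another 50/50 chance of gaining entry into the attendance incentives group following entry into the Walden House program". The same list says "The Attendance intervention lasts for up to 22 weeks" and that earning starts on the Monday after entry into the Attendance Phase. The text then covers the attendance information session and its $20 card, the attendance vouchers, and a bonus for HIV testing. It states no attendance voucher amounts.
- **Reinforcement Schedule, Attendance Phase paragraph.** A parenthesis says: "Participants will be made fully aware that they have only a 50/50 chance of receiving monetary rewards for either Admission phase or Attendance phase".

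**The concern.** The protocol identifies a threat to its own admission outcome and guards against it in one document, the consent form. It then scripts an oral description that gives away the same information minutes later. Admission is one of the two primary aims for which the study is powered (Power Analysis), and H1 compares show-up between the Admission Incentive and Admission Information groups.

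If recruits in both groups know that reaching Walden House opens a second draw for vouchers, the Information group is no longer a group without a financial reason to show up. The historical 56% show-up rate (Conception of the Problem Addressed) may then not describe it, and the contrast may shrink. Interviewers who follow the consent rationale and those who follow the intake list would also tell recruits different things. No analysis can undo the disclosure once it is made.

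**Working it through.** **1. Do the passages conflict?**

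- The consent item literally restricts only the form. Its stated reason concerns show-up behavior, and an oral description straight after signing defeats that reason just as a written one would.
- The phrase "During both the Admission and Attendance phases, a brief description of that phase's incentive program" points to phase-specific content, but the list that follows is a single block. Nothing in it is marked for one phase or withheld from Admission recruits.
- The two-draw sentence makes sense only for someone who has not yet reached Walden House, because it places the second draw after entry to the program.
- Other lines, such as the Monday start and the information session, fit only people already at Walden House. The block therefore reads as two scripts merged into one.

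**2. Do both arms hear it?** Yes. The description precedes the baseline interview. The Lifestyle Criminality Screening Form is a baseline instrument (Table 4) and its score is an urn variable (Randomization), so Admission randomization follows the baseline interview. Exposure is therefore the same in both arms.

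**3. What is the prospect worth?** The script gives no voucher amounts. Intervention Cost gives a maximum of $882.50 and an estimated average of about $500 in the Attendance Incentive group:

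- average: 0.5 × 500 = $250
- maximum: 0.5 × 882.50 = $441.25

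The Admission voucher under test is $50.

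**4. The plan's own sample size.** Inputs are N = 250 at 1:1 allocation, so 125 per arm; two-sided alpha .05; power .80; base rate 56%. The protocol gives no numeric effect for admission, so N = 250 can be checked for consistency but not reproduced exactly. With the arcsine effect size h:

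- minimum detectable h = (1.960 + 0.842) × √(2/125) = 0.354
- the rate at that distance from 56% is sin²[(2·arcsin√0.56 + 0.354)/2] = 0.7285, or 72.9%

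This fits the low-medium effect that the protocol assumes. It is the reference case with disclosure withheld.

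**5. If disclosure raises show-up.** The size of the rise is not in the protocol; 3 to 10 points is an assumption, as is the Incentive arm's share of it. Power uses the pooled-variance normal approximation:

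power = Φ[(d − 1.96·SE₀)/SE₁], with SE₀ = √(p̄(1−p̄)·2/125) and SE₁ = √((p₁(1−p₁) + p₂(1−p₂))/125).

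Example, 61% against 72.85%: d = 0.1185, SE₀ = 0.0595, SE₁ = 0.0590, power ≈ .51.

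| Rise in Information arm | Incentive arm unchanged | Incentive arm rises half as much | Incentive arm rises equally |
|---|---|---|---|
| 0 points (56%) | .80 | .80 | .80 |
| 3 points (59%) | .64 | .73 | .82 |
| 5 points (61%) | .51 | .69 | .83 |
| 8 points (64%) | .32 | .61 | .85 |
| 10 points (66%) | .22 | .55 | .87 |

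Power falls only where the Information arm gains more than the Incentive arm. With equal gains it rises slightly, because the variance is smaller at higher proportions.

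**The case against.** The best defense is that the description is limited by its own opening to the incentive program of the phase at hand. On that reading a sensible interviewer at the prison would leave out the attendance material, and the fault is loose drafting of a shared block. Part of this stands: the text is a shared block, and some of its lines cannot apply in prison. It does not remove the conflict, because the sentence naming both draws is the one that best fits a prison recruit.

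Four stronger readings are tempting, and the document does not support them.

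- **That H1 is biased or its type I error inflated.** Both arms receive the same information before randomization, so the randomized contrast remains valid.
- **That recruits are told of $882.50.** The maximum appears in the voucher introduction, the incentive schedule and the cost section, not in the intake description. The protocol's own average puts the prospect nearer $250 than $441.
- **That power falls to .51 or .22.** Those figures assume that the disclosure moves only the Information arm, although both arms hear it. They also start from the smallest effect with 80% power. At a conventional medium h of 0.50 (56% against 79.1%), the same 5-point case with the Incentive arm unchanged still has power of about .88.
- **That the Reinforcement Schedule parenthesis shows disclosure in prison.** It sits in the Attendance Phase paragraph and gives no timing. It can mean that participants in each phase are told that phase's odds.

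**Conclusion.** The inconsistency is real and should be resolved before the script is used. The consent item and the intake list cannot both serve the stated aim of keeping the attendance incentives from affecting show-up.

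If the intake list is followed as written, H1 still tests the $50 voucher, but on top of a known chance of further vouchers and probably from a base rate above 56%. A reader might infer that Aim 1 goes unanswered. That is too strong: an incentive is still being tested, in a changed context.

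The change of context follows from the text alone. Loss of power does not: it depends on how much show-up rises and on how the rise is shared between arms, and the protocol gives neither. Over assumed rises of 3 to 10 points in the Information arm, power runs from .22 to .64 if the Incentive arm does not rise, from .55 to .73 if it rises half as much, and is not reduced if it rises equally.

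**What to change.** Split the intake description into two versions.

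- **Admission version (prison).** Keep the admission 50/50 statement. Remove the attendance draw, the 22-week line, the Monday-start line, the attendance information-session and voucher text, and the HIV bonus.
- **Attendance version (Walden House).** Keep the removed material here, and describe only the attendance draw as still to come.

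In the Reinforcement Schedule, reword the parenthesis on 50/50 odds so that participants in each phase are told that phase's odds.

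The cost is script wording and a short instruction to interviewers. Sample size, randomization and analysis do not change. By the protocol's own account the Admission consent form already leaves the Attendance Phase out, so the change brings the oral description into line with it.

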(the following is an adapted excerpt from the HAART Manual, pp.757-760)

“For optimum effectiveness, reinforcement should be applied as soon as possible following the target behavior. The schedule of reinforcement makes a difference in the effectiveness of the reinforcement program. In a continuous reinforcement schedule, a response is reinforced each time it occurs, such as receiving a voucher for each day of attendance. The advantage of continuous reinforcement is that performance occurs at a high level while behavior is being reinforced,” (Haug, et. al., 2006).

“The *schedule of reinforcement* refers to the temporal relationship between the target behavior and the delivery of consequences,” (Haug, et. al., 2006). An escalating schedule involves increasing the monetary value of the vouchers as the number of consecutive target behaviors (e.g., attendance at Walden House treatment sessions) increases. This system also includes a “reset” function when clients do not achieve the target behavior: The voucher value is reset to the initial low value (\$2.50) following noncompliance, but clients have the opportunity to build back their earnings. Participants who accomplish 10 days of scheduled treatment attendance in a row (6 contacts for outpatients), following a skipped treatment day, resume earning at the next highest level greater than the level previously achieved. The reset function must always begin on the Monday following a client’s return to treatment. For example, if a client returns on a Thursday, then he will begin his 2 weeks of reset earnings on the following Monday and will earn nothing for Thursday and Friday.

Admission Phase - Study participants in the Admission Incentive group will receive a voucher of \$50 if they show up at the Walden House program, complete the intake process, and remain at Walden House for at least 48 hours. In order to encourage prompt enrollment, participants will receive the incentive only if they show up at the Walden House program within two weeks following the date of their release from incarceration (but they will still have the opportunity to participate in the Attendance Phase). Participants in the Admission Information group will not receive a voucher for enrolling in community treatment.

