- 7) interviewers administer the appropriate research documentation forms (see Assessment – Research Documentation Forms section)
- 8) interviewers look for reporting inconsistencies and socially desirable responses; and
- 9) consistency checks on reporting are built in as part of the interview process.

The Project Director will periodically sit in on interviews to ensure compliance with interview protocols and to identify problems that need correction. As a quality check, the Project Director will randomly call 10% of participants for whom interview forms are on file to verify that the interview took place and to ask about suggestions on interview procedures (see ISAP's data integrity policy in Appendix C).

RANDOMIZATION

In the Admission Phase, clients will be randomized to the Admission Incentive group or to the Admission Information group. Thus, each client has a 50/50 chance of gaining entry to the Incentive group or the Information group. Those clients in the Admission Phase who show up at Walden House and complete intake process will be consented and re-randomized to the Attendance Incentive group or to the Attendance Information group. In both cases, clients will

be randomly assigned to one of the study conditions using the Urn Randomization Program (version 1.10, developed at Yale University for Clinical Trials Network studies). Urn randomization is a procedure to maintain balance and minimization of bias across study groups for selected characteristics expected to be related to outcome (Stout, Wirtz, Carbonari, & Del Boca, 1994). The following baseline variables that are strongly associated with drug use and/or crime outcomes will be used in urn randomization:

- Race/ethnicity (African American vs. White/Hispanic/Other)
- Risk for recidivism (using the score on the Lifestyle Criminality Screening Form: 0-7 vs. 8-20)
- Parole status (In-Custody Drug Treatment Program vs. voluntary SAP graduate) – because custody arrangements differ between the two groups. In-Custody Drug Treatment Program (ICDTP) clients are considered to be in-custody and cannot leave the program premises without a staff member, while voluntary SAP graduates are not required to stay in the program.

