RQ2. Were treatment staff members able to adhere to the procedures of the Contingency Management Manual?

RQ3. Were there programmatic, logistic, or other issues that facilitated or compromised the implementation of the intervention?

RQ4. What factors are likely to promote or impede the sustainability of the CM intervention beyond the end of the study?

QUANTITATIVE ANALYSES

Overview. Consideration of specific aims, hypotheses, data structures, and available resources will determine the choice of analytic approaches. Analyses will examine both significant differences (if any) between the groups on the outcomes of interest and the magnitude of the difference (i.e., effect size). The main analyses will follow the “intent-to-treat” approach in which we will include all clients in the analysis for whom data are available, whether they have completed treatment or not (Nich & Carroll, 2002). Methods that provide unbiased effects in the face of non-compliance (e.g., Complier Average Causal Effect analysis) may also be used. The following discussion covers power analysis, preliminary and descriptive analyses, design analyses, hypothesis testing, and other analyses.

POWER ANALYSIS

The study is powered for the two primary aims: whether incentives increase admission and whether they increase attendance. Two meta-analyses of contingency management have found that the average effect size for outcomes measured during or at the end of treatment is in the medium range (using Cohen’s guidelines; Cohen, 1988). Lussier et al. (2006) reported an average effect size (using a random effects model) for abstinence outcomes of $d = 0.67$ (transformed from $r = 0.32$). Prendergast et al. (2006), using a partially overlapping but larger set of studies, found an effect size (random effects) for drug use outcomes (not necessarily abstinence) of $d = 0.49$. A recent study (Alessi, Hanson, Wieners, & Petry, 2007) examined the effects of CM (using prize-based incentives) on group therapy attendance over 12 weeks, reporting an effect size of $r = .17$ ($d = 0.34$). CM studies have not examined the effect of incentives on enrollment in treatment or on attendance over longer periods of time (e.g., 26

weeks), but it is reasonable to assume that effect sizes for these outcomes would also be in the low medium range.

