For the primary outcomes of admission and attendance, there will be no attrition since these outcomes will be based on program records. For the Admission Phase, the target sample size of 250 will allow detection of medium effects in comparisons between groups on the percentage of clients who enroll in treatment at Walden House, with $\alpha = .05$ (two-tailed) and power .80. For the Attendance Phase, with retention as the outcome, the sample size of 200 will allow detection of similar effects between groups. For the 12-month outcomes, the effect size will be smaller, possibly around $d = 0.30$, based on a previous meta-analysis of drug abuse treatment generally (Prendergast, Podus, Chang, & Urada, 2002). Here, where the analysis will be based on the follow-up interview sample in the Attendance Phase (~170), power is likely to be about .75. For arrest and reincarceration, where there will be no attrition, power will be at least .80. Inclusion of covariates may increase power somewhat (Tabachnick & Fidell, 1996).

PRELIMINARY AND DESCRIPTIVE ANALYSES

As noted above, faxable forms will allow many of the instruments to be quickly entered and checked, making it possible to periodically examine the data. Descriptive statistics on variables of interest will include percentages, means, correlations, measures of variance, and distribution characteristics, as appropriate to the measurement level of selected variables. Frequency tables will be used to examine cell sizes for categorical variables and non-normality for continuous variables. Where categorical variables have small cell sizes, we will collapse the categories where possible to create cells of sufficient size. Where variables are non-normally distributed, we will transform the variable if possible or use a non-parametric approach. If outliers are present, they may be recoded or omitted. Descriptive analyses will provide statistics on treatment-related variables, including percentage of sessions attended, number of weeks attended, value of vouchers earned, and items for which vouchers were redeemed.

DESIGN ANALYSES

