Although the validity of self-report by clients of their behavior is often in question, prior research indicates that self-report interviews, when properly conducted, are generally reliable and valid in measuring drug and alcohol use (Buchan, Dennis, Tims, & Diamond, 2002; Chou, Hser, & Anglin, 1996; Darke, 1998) and criminal involvement (Elliot, Huizinga, & Ageton, 1982; Junger-Tas & Marshall, 1999; Thornberry & Krohn, 2000). Biological-based data increases the credibility of findings from self-report, but such data cannot reveal distant use or long-term patterns of use, nor can criminal justice records verify criminal behavior that does not come to official attention. Still, policy makers prefer objective measures of criminal justice involvement to self-reported measures. For the proposed study, we will use several procedures to increase the reliability and validity of self-report data. First, interviewers will assure participants that information that they provide as part of research will not be revealed to parole or other agencies, will not become part of their parole or treatment records, and is protected by a certificate of confidentiality. Second, interviewers will inform participants at the start of the follow-up interview that they will be asked to provide a urine specimen after the interview that will be tested for illicit drugs. Third, with respect to criminal justice system involvement, we will obtain official arrest and incarceration records from the California Department of Justice and the California Department of Corrections and Rehabilitation, which can be used to verify self-reported arrest and incarceration.

HYPOTHESIS TESTING

For the Admission Phase, the independent variables are Admission Incentive vs. Admission Comparison. For the Attendance Phase, the independent variables are Attendance Incentive vs. Attendance Comparison.

Primary dependent variables will be the proximal outcomes of treatment admission and retention. Secondary dependent variables will be the distal outcomes of substance use, crime, and psychosocial functioning, including employment, education, family relationships, psychological functioning, and HIV risk.

Treatment admission. Whether study participants completed intake for admission to the Walden House residential program and the outpatient program will be based data from program records. Time to admission, calculated from date of parole release to date of enrollment, will also be examined.

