Hypothesis tests are based on the assumption of group equivalence due to random assignment. However, if preliminary analysis indicates significant baseline differences, then additional control variables will be included in the analyses. Hypotheses will be tested using a two-sided .05 level of significance.

Hypotheses will initially be tested using t-tests and chi-square tests. T-tests will be used to conduct pairwise comparisons of participants in the study groups on outcomes measured as a single continuous variable. For categorical and binary outcome variables, we will use chi-square analysis. If covariates are required, analyses will be extended to ordinary least squares (OLS) or logistic regression as appropriate to the scale properties of the dependent variable. Because of missing data, inclusion of covariates, and/or repeated measures for binary outcomes, analyses may be extended to generalized linear models (McCullagh & Nelder, 1989). Structural equation modeling will be used to determine whether the effect of incentives on distal outcomes is mediated by program admission, treatment activities, admission, or retention (Kaplan, 2000).

For each hypothesis, an effect size will be calculated. The index of effect size will be the standardized mean difference (calculated as the difference between two groups divided by the pooled standard deviation); for proportions, the equivalent effect size is calculated using the arc sine transformation (Lipsey & Wilson, 2001). An effect size for study outcomes will provide a

quantitative indication of the magnitude of the difference between groups; it will also be useful in calculating power for any future study of this intervention.

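### The Attendance Phase urn and covariate rule leave out Admission Phase assignment: no bias to H3, but a cheap gain in balance, precision and interpretability is missed

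*Protocol*

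**What the plan says.** Protocol, Randomization: "Those clients in the Admission Phase who show up at Walden House and complete intake process will be consented and re-randomized" to Attendance Incentive or Attendance Information. Under Recruitment - Intake Procedures, other eligible arrivals at Walden House enter the same randomization, so the Attendance Phase pools former Admission Incentive clients, former Admission Information clients and direct entrants.

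The urn factors are introduced with "The following baseline variables that are strongly associated with drug use and/or crime outcomes will be used in urn randomization". They are race/ethnicity, LCSF score and, for the Attendance Phase only, parole status (In-Custody Drug Treatment Program against voluntary SAP graduate). The same section explains that parole status is not used in the Admission Phase because every man leaving SATF for Walden House falls in the voluntary level.

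Reinforcement Schedule: the $50 admission voucher requires arrival within two weeks of release, completed intake, and that the client "remain at Walden House for at least 48 hours".

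Hypothesis Testing: "For the Attendance Phase, the independent variables are Attendance Incentive vs. Attendance Comparison". Testing starts with t-tests and chi-square tests and moves to regression if covariates are needed. Design Analyses sets the covariate rule: selected baseline variables are compared between arms, those that differ significantly enter a logistic model for group membership, and the significant predictors become covariates. The examples given are age, race/ethnicity, main drug and motivation. Admission Phase assignment is neither named nor excluded.

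**The concern.** An earlier randomized assignment is an obvious candidate for balancing a later randomization in the same trial: it is recorded, free of missing data and set by the study itself. There is reason to expect a link with retention. H1 predicts that the voucher brings in men who would otherwise not come, so the make-up of arrivals would depend on Admission arm. The protocol already recognizes influence between phases in the other direction: the Admission consent form leaves out the Attendance Phase because the prospect of further incentives might raise show-up.

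The listed urn factors were chosen for their link with drug use and crime, whereas the primary Attendance outcome (H3) is retention. At stake are some balance and precision in H3, and the ability to see whether attendance vouchers work differently in men who had been offered payment to enroll.

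**Working it through.** **Inputs from the protocol**
- Attendance Phase N = 200, 1:1, so 100 per arm: "For the Attendance Phase, with retention as the outcome, the sample size of 200 will allow detection of similar effects between groups" (Power Analysis).
- Test level: "Hypotheses will be tested using a two-sided .05 level of significance" (Hypothesis Testing).
- Power: "two-tailed) and power .80", stated for the Admission Phase and carried over to Attendance as similar effects.
- Effect size: "it is reasonable to assume that effect sizes for these outcomes would also be in the low medium range". No single d is fixed.
- Admission Phase N = 250 (Power Analysis) and show-up of about 56% (Conception of the Problem).

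**Assumptions (not in the protocol)**
- All arrivals consent.
- Carry-over c is the shift in mean retention, in SD units, among former Admission Incentive clients.
- K is the number of the 200 who come from the Admission Incentive arm. The base case is 250 × 0.56 / 2 = 70. If that arm shows up at 70%, K = 125 × 0.70 = 87.5, about 88. The range examined is 62 to 100.

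**Step 1. The plan's own figure.** Detectable d = (1.960 + 0.842) × √(2/100) = 0.396. This fits the stated low-medium to medium range, so the claim for N = 200 reproduces. The standard error of d is √(2/100) = 0.141.

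**Step 2. Chance imbalance.** With p = K/200, the SD of the between-arm difference in share is 2√(p(1−p)/199).
- K = 70: SD 0.068, 95% range ±13 points.
- K = 62 to 100: SD 0.066 to 0.071, 95% range about ±13 to 14 points.

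This treats the urn as simple equal allocation. If all 60 direct entrants were in-custody clients and parole status were perfectly balanced, the K = 70 range would shrink to 1.96 × √(0.25 × 2/70) × 0.70 = 11.6 points.

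**Step 3. What the imbalance does to H3.** The shift in d is the imbalance times c. The 95% ranges at K = 70 are:
- c = 0.1: ±0.013
- c = 0.2: ±0.027
- c = 0.3: ±0.040
- c = 0.5: ±0.066, which is 0.47 of the standard error

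**Step 4. When the covariate rule would react.** At p = 0.35 the standard error of the difference is √(0.35 × 0.65 × 2/100) = 0.0675, so significance needs 1.96 × 0.0675 = 13.2 points. A split of 42 against 28 (14 points, z = 2.08) would be flagged. A split of 41 against 29 (12 points, z = 1.78) would not, and at c = 0.5 would leave a shift of 0.12 × 0.5 = 0.06 d unadjusted. Because allocation is random, such a screen fires in only about 5% of trials.

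**Step 5. Simulation** (20,000 trials per setting, K = 70).

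| c | true d | Unadjusted | Adjusted | Stratified and adjusted |
|---|---|---|---|---|
| 0.2 | 0 | 0.052 | 0.051 | 0.049 |
| 0.5 | 0 | 0.050 | 0.051 | 0.050 |
| 0.2 | 0.396 | 0.795 | 0.795 | 0.796 |
| 0.5 | 0.396 | 0.776 | 0.799 | 0.800 |

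Entries are rejection rates. Mean bias of the unadjusted estimate is 0.00 throughout. The gain is 0.1 points at c = 0.2, within simulation error, and 2.4 points at c = 0.5 (0.79985 − 0.77575). Nearly all of the latter comes from adjustment.

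**Step 6. Effect modification (illustration, assumed effects).** Suppose d = 0.2 in former Admission Incentive clients and 0.5 in everyone else. The pooled effect is 0.35 × 0.2 + 0.65 × 0.5 = 0.395 at a 35% share and 0.44 × 0.2 + 0.56 × 0.5 = 0.368 at 44%. The pooled test cannot reveal such a difference.

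**The case against.** The best defence is that randomization already does the job. The second allocation is independent of the first, so admission history is balanced on average and the ordinary standard error covers its chance imbalance, as for any unstratified variable. That stands in full. A reader might infer that carry-over from the admission voucher biases H3; the design does not allow that inference, and Step 5 shows neither bias nor excess type I error.

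Second, the protocol has a safeguard. The baseline equivalency analysis has an open list, and Hypothesis Testing allows added control variables. The sentence on independent variables names the randomized contrast and does not say that arm is the only model term. This also stands, but the stated rule is conditional on significance and would rarely bring in Admission arm.

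Third, a prespecified covariate and a subgroup report could sit in an analysis plan that is not shown. True, but the urn list and the significance-based rule are fixed in the protocol.

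Fourth, the mechanism may be weak. The voucher is earned after 48 hours and Attendance randomization may come up to a week after intake, so men who leave once paid may never enter H3. No document gives a carry-over size. This is why the result is shown as a range.

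Fifth, parole status does separate in-custody direct entrants from SATF arrivals. It fails between the two Admission arms and for the other direct entrants.

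**Conclusion.** The point holds as a low-severity improvement. Admission Phase assignment is known at the second randomization, is plausibly related to retention, is not balanced by any listed factor across the two Admission arms, and would be adjusted for only after a significant imbalance of roughly 13 points. The cost is about 0 to 2.4 power points for an assumed carry-over of 0.2 to 0.5 SD at K = 70, plus no stated look at whether the attendance effect differs by admission history.

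Two stronger readings are not supported. A reader might take 13 to 14 points as a ceiling or as an effect on the outcome. It is the 95% range of chance imbalance in a share, and it moves H3 by only about 0.03 to 0.07 d against a standard error of 0.141. A reader might also fault the Attendance Information group for containing men already paid for admission. The protocol never claims that group is free of incentives (it receives a $20 card for the information session), H3 contrasts attendance vouchers with none, and earlier payments are expected equally in both arms.

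**What to change.** - **Randomization:** add a fourth urn factor for the Attendance Phase only, Admission Phase assignment, with three levels (Admission Incentive, Admission Information, not in the Admission Phase).
- **Design Analyses and Hypothesis Testing:** state that this factor is a covariate in H3 and in the 12-month Attendance comparisons whatever the baseline significance test shows, using the linear or logistic regression already foreseen.
- **Other Analyses:** report the Attendance effect by this factor descriptively, without a formal claim, since 200 clients split three ways cannot support one.

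The cost is one more urn entry from data the study already holds and one three-level model term. The downside is slightly looser urn balance on the other three factors. If the urn can no longer be changed, the covariate alone recovers almost all of the precision (0.799 against 0.800 at c = 0.5).
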